7.2 Medical History

Medical history data will be coded using the MedDRA coding dictionary; the actual version of the MedDRA coding dictionary will be noted in the clinical study report. Medical history data will be summarized and presented using MedDRA System Organ Class (SOC) and preferred term. The SOCs will be presented in alphabetical order, and the preferred term will be presented in alphabetical order within each SOC. The number and percentage of subjects with a particular preferred term will be summarized for each treatment arm. Subjects reporting more than one preferred term within each SOC will be counted only once for that SOC.

7.3 Prior, Concomitant and Post-Treatment Medications

A prior medication is defined as any medication taken prior to the date of the first dose of DB study drug (ABT-493/ABT-530 or placebo). A concomitant medication is defined as any medication that started prior to the date of the first dose of DB study drug and continued to be taken on or after the first dose of DB study drug or any medication that started on or after the date of the first dose of DB study drug, but not after the date of the last dose of study drug (DB or OL). A post-treatment medication for the treatment of HCV is defined as any medication taken on or after the last dose of study drug and entered as "Post-treatment HCV medications" on the eCRF.

Hepatoprotective medications taken at baseline will be summarized by generic drug name for each treatment arm.

Prior medications will be divided into the following categories:

- Prior HCV medications taken by treatment-experienced subjects;
- Prior HIV medications taken by HCV/HIV co-infected subjects receiving ART (as determined by investigator on concomitant medication eCRF) at baseline;
- All other prior medications for all treated subjects.

Concomitant medications will be divided into the following categories:

- Concomitant HIV medications taken by HCV/HIV co-infected subjects;
- All other concomitant medications for all treated subjects.

The number and percentage of subjects taking prior medications, concomitant medications, and post-treatment HCV medications will be summarized for each treatment arm by generic drug name based on the WHO Drug Dictionary.

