4.2 Design Diagram

This is a Phase 3, randomized, double-blind, placebo-controlled multicenter study to evaluate the efficacy and safety of ABT-493/ABT-530 in non-cirrhotic chronic HCV GT1 to GT6-infected Asian adult subjects with or without HIV co-infection who are HCV treatment-naïve or treatment-experienced with IFN (alpha, beta or pegIFN) with or without RBV OR sofosbuvir with RBV with or without IFN. This study consists of a Double-Blind (DB) Treatment Period, an Open-Label (OL) Treatment Period, and a Post-Treatment (PT) Period. The study schematic is presented in [Figure 1](#).

The study is designed to enroll approximately 504 subjects to meet scientific and regulatory objectives without enrolling an undue number of subjects in alignment with scientific and ethical considerations. A minimum of 150 GT1-infected subjects, a minimum of 150 GT2-infected subjects and approximately 60 GT3, 4, 5 or 6-infected subjects from China will be enrolled into this study. Approximately 105 GT1-infected subjects and approximately 39 GT2-infected subjects will also be enrolled into this study from the regional Asian countries of South Korea and Singapore. Of the approximately 504 subjects, a maximum of 50 HCV/HIV co-infected subjects will be enrolled.

Figure 1. Study Schematic

Chronic HCV GT1 – 6 infected adults without underlying cirrhosis will be enrolled into one of two treatment arms:

Arm A: ABT-493/ABT-530 300 mg/120 mg QD for 8 or 16 weeks

Arm B: Matching Placebo for 8 or 16 weeks followed by open-label ABT-493/ABT-530 300 mg/120 mg QD for 8 or 16 weeks

All subjects in this study are to be non-cirrhotic. Treatment experienced GT3-infected subjects will receive 16 weeks of treatment in the DB and/or OL Treatment Period; all other subjects will receive 8 weeks of treatment in the DB and/or OL Treatment Period.

In China, subjects will be randomized to receive active treatment (Arm A) or placebo (Arm B) in a 2:1 ratio for each of the GT1 and GT2-infected groups and the combined GT3 to GT6 infected group. In each regional Asian country, each of the GT1 and GT2 infected groups will be randomized in a 2:1 ratio.

Subjects who are randomized to Arm B will receive open-label ABT-493/ABT-530 300 mg/120 mg QD for 8 or 16 weeks following the DB Treatment Period.

Randomization of subjects will be stratified by geographic region (China, Singapore and South Korea), genotype (GT1, GT2, combined GT3 – 6), and HCV/HIV co-infection status (yes, no).

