4.4 Planned Analyses

The primary analysis will occur after all subjects in Arm A have completed the PT Week 12 Visit or prematurely discontinued the study. The primary analysis will summarize data through PT Week 12 for Arm A subjects and data through the DB Treatment Period for Arm B subjects. The data for the primary analysis will be locked after data cleaning, and data collected after this lock will be added to a new version of the database. Results from the primary analysis will be described in the primary clinical study report (CSR) and submitted to regulatory agencies as part of an NDA submission.

An interim analysis will occur after all Arm A subjects have completed the PT Week 24 Visit or prematurely discontinued the study and all Arm B subjects have completed the PT Week 12 Visit or prematurely discontinued the study. The data for the interim analysis will be locked after data cleaning, and data collected after this lock will be added to a new version of the database.

The final analysis will be conducted after all subjects enrolled in the study have completed the PT Week 24 Visit or prematurely discontinued the study. The data for the final analysis will be cleaned and locked at the end of the study and included in the final CSR.

All analyses will be conducted by statisticians and programmers at AbbVie (or their designees) according to the methodologies specified in this SAP. There is no intention of shortening the follow-up time of subjects based on efficacy findings from the primary or interim analyses. All subjects who receive active study drug will be followed for 24 weeks following treatment. Therefore, no statistical adjustment will be employed due to the primary or interim analysis.

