7.0 Demographics, Baseline Characteristics, Medical History, and Other Medications

The safety population (and ITT population if it differs from the safety population) will be used to summarize demographics and baseline characteristics by treatment arm (Arm A and Arm B) and across the treatment arms for the set of all subjects, for each of the GT1-infected and GT2-infected groups, and for the geographic region of China during the DB Treatment Period. In addition, demographics and baseline characteristics will be summarized for the geographic region of China for each of the GT1-infected and GT2-infected groups.

The safety population will be used to summarize medical history and previous, concomitant, and PT medications by treatment arm and across the treatment arms for the set of all subjects and for the geographic region of China.

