7.1 Demographic and Baseline Characteristics

Categorical demographic and baseline characteristic variables will be summarized with the number and percentage of subjects in each category and proportions will be compared between the treatment arms with a chi-square test. Continuous variables will be summarized with descriptive statistics (number of non-missing observations, mean, standard deviation, median, maximum and minimum), and means will be compared between the treatment arms with a one-way analysis of variance (ANOVA).

Continuous demographic variables include age, weight, height, waist circumference, and body mass index (BMI). Categorical demographic variables include sex, age category (< 65 or ≥ 65 years; < 75 or ≥ 75 years), BMI category (< 25, ≥ 25 to < 30, or ≥ 30 kg/m²), race, ethnicity, type of Asian descent (Chinese, Korean, Malay or Other), and geographic region.

Continuous baseline characteristics include baseline log₁₀ HCV RNA level, homeostasis model of assessment – insulin resistance (HOMA-IR), platelet count, albumin, GGT, LDL, HDL, total insulin, APRI, FIB-4, AST, ALT, AST/ALT ratio, creatinine clearance

(by Cockcroft-Gault formula, defined below), eGFR (using the modification of diet in renal disease [MDRD] formula modified for the Chinese population [C-MDRD], defined below), total, direct, and indirect bilirubin, total international normalized ratio (INR).

Categorical baseline characteristics include:

- HCV genotype (1, 2, 3, 4, 5, or 6) and available subtype (as determined by the central laboratory);
- HCV genotype (1, 2, 3, 4, 5, or 6) and available subtype (final HCV genotype and subtype as defined in Section 10.8);
- Prior HCV treatment history (naïve or experienced);
- HCV genotype (1, 2, 3, 4, 5, or 6) (as determined by the central laboratory) and prior HCV treatment history;
- HCV genotype (final HCV genotype as defined in Section 10.8) and prior HCV treatment history;
- For treatment-experienced subjects, type of prior treatment experience (IFN-based or SOF-based; subjects who received SOF will be categorized as SOF-based);
- For treatment-experienced subjects, type of non-response to previous treatment (on-treatment nonresponder or breakthrough, post-treatment relapse, or unknown/other);
- Screening HIV co-infection status (HCV mono-infected or HCV/HIV co-infected);
- IL28B genotype (CC, CT, or TT; CC or non-CC);

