- Baseline HCV RNA level ($< 1,000,000$ or $\geq 1,000,000$ IU/mL; $< 6,000,000$ or $\geq 6,000,000$ IU/mL; $< 10,000,000$ or $\geq 10,000,000$ IU/mL);
- Baseline HOMA-IR (< 2 or ≥ 2 mU \times mmol/L²);
- Baseline fibrosis stage (equivalent to Metavir F0 – F1, F2, F3, F4 [if applicable]);
- Baseline platelet count (< 100 or $\geq 100 \times 10^9$ /L);
- Baseline albumin (< 35 or ≥ 35 g/L);

- Baseline creatinine clearance (Cockcroft-Gault) (< 60 , ≥ 60 to < 90 , or ≥ 90 mL/min);
- Baseline eGFR (C-MDRD) (< 60 , ≥ 60 to < 90 , or ≥ 90 mL/min/1.73 m²);
- Baseline total bilirubin (< 34.2 or ≥ 34.2 umol/L);
- Baseline total INR (continuous and < 1.7 or ≥ 1.7);
- History of diabetes (yes/no);
- History of bleeding disorders (yes/no);
- History of depression or bipolar disorder (yes/no);
- History of cardiovascular disease (yes/no);
- Baseline metabolic syndrome (yes/no);
- Injection drug use (yes, within last 12 months; yes, more than 12 months ago; or no);
- Baseline stable opiate substitution use (yes/no);
- Baseline hepato-protectant medication use (as determined by investigator on concomitant medication eCRF, yes/no);
- Tobacco use (user, ex-user, or non-user);
- Alcohol use (drinker, ex-drinker, or non-drinker);
- Concomitant use of Proton Pump Inhibitors (PPIs) (yes/no).

The demographic and baseline characteristics specified above, along with the following, will be summarized for subjects with HCV/HIV co-infection at Screening for the overall safety population and for the geographic region of China:

- HIV-1 treatment status (antiretroviral therapy [ART]-Naïve, ART-Treated),
- HIV-1 ART regimen (e.g., raltegravir [RAL], dolutegravir [DTG], rilpivirine [RPV]) for those receiving ART (as determined by investigator on concomitant medication eCRF) at baseline,
- Baseline CD4+ T-cell count (continuous; and < 200 , 200 to < 350 , 350 to < 500 , or ≥ 500 cells/mm³).

Any concomitant medication coded to the WHO Drug Dictionary ATC code of A02BC will be counted as a PPI.

If the IL28B genotype result is not available from a sample collected during the Screening period, then a result available from a sample collected at any time during the study will be used to summarize IL28B genotype.

HOMA-IR is defined as fasting glucose (mmol/L) \times fasting insulin (μ IU/mL) \div 22.5. Subjects who do not have concurrent fasting glucose and fasting insulin values at baseline will be excluded from the summary of baseline HOMA-IR.

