10.6 Efficacy Subgroup Analysis

Subgroup analyses will be performed for the primary efficacy endpoint of SVR₁₂.

Within each subgroup, the number and percentage of Arm A subjects achieving SVR₁₂ will be calculated for the set of all subjects in the ITT population and for each of the GT1-

infected and GT2-infected groups. The 2-sided 95% Wilson score CI will be produced if there are at least 10 subjects in the subgroup.

The following subgroups will be analyzed:

- HCV genotype and available subtype (based on the latest determination of genotype from the baseline sample [by the central laboratory or by phylogenetic analysis, with preference given to the phylogenetic analysis results] at the time of the primary SVR₁₂ analysis);
- Prior HCV treatment history (naïve or experienced);
- For treatment-experienced subjects, type of prior treatment experience (IFN- or SOF-based);
- For treatment-experienced subjects, type of non-response to previous treatment (on-treatment nonresponder or breakthrough, post-treatment relapse, or unknown/other);
- Screening HIV co-infection status (HCV mono-infected or HCV/HIV co-infected);
- IL28B genotype (CC or non-CC);
- Sex (male or female);
- Age (< 65 or ≥ 65 years) and (< 75 or ≥ 75 years);
- Geographic region (China, Singapore, or South Korea);
- Type of Asian descent (Chinese, Korean, Malay, or Other);
- Baseline BMI (< 30 or ≥ 30 kg/m²);
- Baseline HCV RNA level (< 1,000,000 or ≥ 1,000,000 IU/mL; < 6,000,000 or ≥ 6,000,000 IU/mL; < 10,000,000 or ≥ 10,000,000 IU/mL);
- Baseline HOMA-IR (< 2 or ≥ 2 mU × mmol/L²);
- Baseline fibrosis stage (equivalent to Metavir F0 – F1, F2, F3, F4 [if applicable]);
- Baseline platelet count (< 100 or ≥ 100 × 10⁹/L);
- Baseline albumin (< 35 or ≥ 35 g/L);
- Baseline creatinine clearance (< 60, ≥ 60 to < 90, or ≥ 90 mL/min);

- Baseline eGFR (C-MDRD) (< 60, ≥ 60 to < 90, or ≥ 90 mL/min/1.73 m²);
- History of diabetes (yes/no);
- History of bleeding disorders (yes/no);
- History of depression or bipolar disorder (yes/no);
- History of cardiovascular disease (yes/no);
- Baseline metabolic syndrome (yes/no);
- Injection drug use (yes, within last 12 months; yes, more than 12 months ago; or no);
- Baseline stable opiate substitution use (yes/no);
- Baseline hepato-protectant medication use (yes/no);
- Study drug compliance (yes/no);
- Concomitant use of PPIs (yes/no).

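### SAP 7.3 runs the concomitant-medication window through open-label dosing with no split by period, and SAP 7.1 tests on-treatment PPI use between arms as a baseline characteristic

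*SAP*

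**What the plan says.** SAP 7.3 treats as concomitant any medication already in use at the first DB dose and continued, and any medication started from then on, "but not after the date of the last dose of study drug (DB or OL"). It reports numbers and percentages for each treatment arm and names no period. SAP 7.0 likewise plans to summarise "previous, concomitant, and PT medications by treatment arm and across the treatment arms for the set of all subjects", again without a period. SAP 5.1.3 groups these medication analyses by the treatment actually received in the DB period.

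The arms in SAP 4.2 are "Arm A: ABT-493/ABT-530 300 mg/120 mg QD for 8 or 16 weeks" and "Arm B: Matching Placebo for 8 or 16 weeks followed by open-label ABT-493/ABT-530".

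SAP 7.1 puts concomitant PPI use in its list of categorical baseline characteristics, for which "proportions will be compared between the treatment arms with a chi-square test". The coding rule is: "Any concomitant medication coded to the WHO Drug Dictionary ATC code of A02BC will be counted as a PPI". SAP 10.6 uses the item again as an Arm A subgroup factor for SVR12: "Concomitant use of PPIs (yes/no").

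Other sections draw the period boundary. SAP 4.4 limits the primary analysis to "data through the DB Treatment Period for Arm B subjects". SAP 5.1.4 sends all Arm B data from the OL period onward to the OL population. SAP 11.2.1 closes the Arm B adverse-event window before OL Day 1. SAP 9.1, 9.2 and 11.3.2 handle exposure, compliance and laboratory data separately for DB and OL.

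**The concern.** There are two separate faults.

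The first is the window. The medication tables let a reader judge whether background treatment was alike in the two arms during the blinded comparison. If Arm B's count runs on through OL dosing, the placebo column covers twice the time. It also includes drugs started while the subject was on open-label active treatment. Any medication with new starts would then look commoner in Arm B without any difference in background care.

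The second is the PPI item, and it does not depend on the first. A variable that counts a PPI first taken weeks after randomisation is not a baseline characteristic, even if both arms are observed for the same time. Testing it in the baseline table invites the reader to take an on-treatment difference for a failure of randomisation. The two faults compound if OL use is pooled, because the PPI item takes its window from 7.3.

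**Working it through.** The plan gives no figure for this point, so there is none to reproduce. The check has three parts.

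**1. Window length (durations from SAP 4.2).**
- 8-week regimen: Arm A 8 × 7 = 56 days. Arm B (8 + 8) × 7 = 112 days. Ratio 2.0.
- 16-week regimen: Arm A 16 × 7 = 112 days. Arm B (16 + 16) × 7 = 224 days. Ratio 2.0.

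The ratio applies to Arm B subjects who complete OL.

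**2. Could OL data be in the database at the primary lock?** The lock waits for every Arm A subject to reach Post-Treatment Week 12 or leave the study. For an 8-week subject that is week 8 + 12 = 20. An Arm B subject randomised the same day finishes OL at week 8 + 8 = 16, so the OL medication records would normally exist by then. For the 16-week regimen the times are week 28 and week 32, so OL may still be running. A program that applies 7.3 literally, without the data cut in 4.4, could therefore pick up OL medication.

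**3. Effect on the PPI comparison if OL use is pooled.** Inputs:
- Group sizes: 336 and 168 (504 × 2/3 and 504 × 1/3; SAP 4.3 and Table 1).
- Test: Pearson chi-square, two-sided 0.05.
- b = PPI use ongoing at first DB dose, and s = probability that a non-user starts a PPI per 8 weeks. Both are assumptions, since the documents give neither. Ranges used: b 0–10%, s 1–10%, the same in both arms and both periods, with every Arm B subject completing 8 + 8 weeks.

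Formulas:
- One window (Arm A): P = 1 − (1 − b)(1 − s)
- Two windows (Arm B, literal 7.3): P = 1 − (1 − b)(1 − s)²
- Spurious difference: (1 − b)(1 − s)s

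Example, b = 5%, s = 3%:
- Arm A: 1 − 0.95 × 0.97 = 7.85%
- Arm B: 1 − 0.95 × 0.97² = 10.61%
- Difference: 2.76 points

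Rejection rates come from exact enumeration of both binomials, with no true difference in start rates:

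| b | s | Arm A % | Arm B % | Difference (points) | Rejection |
|---|---|---|---|---|---|
| 0% | 1% | 1.00 | 1.99 | 0.99 | 0.167 |
| 0% | 3% | 3.00 | 5.91 | 2.91 | 0.368 |
| 0% | 5% | 5.00 | 9.75 | 4.75 | 0.527 |
| 0% | 10% | 10.00 | 19.00 | 9.00 | 0.796 |
| 5% | 1% | 5.95 | 6.89 | 0.94 | 0.077 |
| 5% | 3% | 7.85 | 10.61 | 2.76 | 0.189 |
| 5% | 5% | 9.75 | 14.26 | 4.51 | 0.333 |
| 5% | 10% | 14.50 | 23.05 | 8.55 | 0.660 |
| 10% | 1% | 10.90 | 11.79 | 0.89 | 0.064 |
| 10% | 3% | 12.70 | 15.32 | 2.62 | 0.135 |
| 10% | 5% | 14.50 | 18.77 | 4.27 | 0.242 |
| 10% | 10% | 19.00 | 27.10 | 8.10 | 0.546 |

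With Arm B's window closed at the end of DB, the expected difference is 0 and rejection is 0.039 to 0.051 over the same range. With PPI use restricted to medication ongoing at first dose, the expected difference is also 0 and rejection is 0.050 to 0.051 for b = 5% or 10%.

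**The case against.** The best defence is that 7.3 only classifies medications over the whole study, while other sections decide which data enter each report. SAP 4.4 cuts Arm B at the end of DB for the primary analysis. SAP 7.0 places the baseline summaries in the DB period and does not confine that wording to one report. SAP 11.1 keeps Arm B OL data out of the primary report's safety summaries, apart from listings of serious adverse events and deaths. On this reading the primary tables have equal windows.

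Much of that stands. A reader might infer that the primary report will show a false imbalance in medication or PPI use. The documents do not support this, because a stated data cut is not overridden by OL records being in the database. The defence is still incomplete. The DB wording in 7.0 sits in the paragraph on demographics and baseline characteristics, while the paragraph on medications has no period. SAP 11.1 speaks for safety analyses. SAP 4.4 sets no DB limit for the interim or final analysis. Nothing in 7.3 points to any of these limits.

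A reader might also infer that the PPI subgroup for SVR12 in 10.6 is distorted. It is not touched by the unequal windows, because it uses Arm A only. Under 7.3, an Arm A PPI user must have taken the drug on or after first dose and started it no later than last dose, so some overlap with active dosing is assured. A minimum overlap would be a design preference. SAP 10.6 also includes study drug compliance, another on-treatment factor.

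Finally, the medication tables carry no test, and the rejection rates depend on assumed inputs. At 1% starts with 5–10% ongoing use, the excess is about 1 point and rarely significant.

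None of this answers the labelling fault in 7.1. The SAP does define baseline use for another drug class: 7.1 and 10.6 list hepatoprotectant use explicitly at baseline.

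**Conclusion.** The point holds in limited form. SAP 7.3 as written gives Arm B subjects who complete OL twice Arm A's window, with the second half on active drug, and must be reconciled with 4.4, 5.1.4 and 11.2.1. If 4.4 and the DB wording in 7.0 are enforced, the exposure is confined to the interim and final medication tables, or to a program that follows 7.3 literally.

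The PPI item in 7.1 is mislabelled whatever the window, because it is a post-randomisation variable tested as a baseline one. If OL use is pooled into it, the bias is upward in Arm B whenever new starts occur. Its size is about 1 to 9 points, with 6% to 80% rejection against a nominal 5%. Those figures rest on the assumed use and start rates, equal rates in both periods, and full OL completion. They show what could happen and do not predict the result.

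The consequences stop at descriptive and baseline tables. No primary or secondary endpoint uses the variable.

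**What to change.** - **SAP 7.3:** restrict the between-arm concomitant-medication table to the DB period, from first to last DB dose and, for Arm B, before OL Day 1. Tabulate OL-period medication (first to last OL dose) separately for the OL population, in line with 5.1.4.
- **SAP 7.1:** define the baseline PPI item as A02BC use ongoing at first DB dose. Alternatively, move it out of the baseline table and its chi-square test.
- **SAP 10.6:** no change is required. The A02BC coding sentence sits in 7.1 but also serves this subgroup, so keep it for on-treatment use and give the two PPI items distinct names.

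The cost is SAP wording, programming and one extra table. Protocol 5.2.3 already requires medication start and end dates through both treatment periods, so no new data are needed.

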8.0 Subject Disposition

The number and percentage of subjects who screen failed for any reason, and for each screen fail reason, will be summarized for all subjects who screen failed and for subjects who screen failed within each geographic region (China, Singapore and South Korea).

8.1 Disposition of Safety Population

The number of subjects in each of the following categories will be summarized by investigator and across investigators for each treatment arm and across treatment arms for the set of all subjects and for the GT1-infected and GT2-infected groups; within these 3 groups of subjects, summaries will also be performed for each geographic region (China, Singapore and South Korea):

- Randomized subjects;
- Subjects who took at least one dose of DB study drug;
- Subjects who completed DB study drug;
- Subjects who prematurely discontinued DB study drug;
- Subjects who took at least one dose of OL study drug;
- Subjects who completed OL study drug;
- Subjects who prematurely discontinued OL study drug;
- Subjects who completed the study;
- Subjects who prematurely discontinued from the study;

- Subjects ongoing in the Post-Treatment Period (if applicable at the time of analysis).

Note that subjects randomized to placebo may prematurely discontinue DB study drug but upon unblinding at the DB Premature Discontinuation visit find that they are on placebo and elect to continue to attend all remaining DB Treatment Period study visits in order to receive OL, active study drug in the OL Treatment Period. For these placebo subjects, reasons for discontinuation from DB study drug will be collected on the DB Study Drug Completion eCRF. If such a placebo subject chooses to continue the DB Treatment Period in order to enter the OL Treatment Period, but then prematurely discontinues from the DB Period, they will be discontinued from the study entirely.

The number and percentage of subjects who discontinued (DB or OL) study drug will be summarized by reason (all reasons) and by primary reason (per eCRF) for each treatment arm and overall for the set of all subjects and for the geographic region of China. Similar summaries will be provided for discontinuations from the study.

The number and percentage of subjects with reported study drug interruptions will be summarized by treatment arm and overall during the DB and OL Treatment Periods for the set of all subjects and for the geographic region of China.

Reasons for study drug interruptions will be presented in the CSR listings.

